may cause scarring and hardening of fatty tissue, which may interfere with the absorption of the drug, and therefore, injections should not be given at the same location repeatedly. Each TAK-510 injection must be administered approximately 2 inches (5 centimeters) apart and must not be administered into an area where the skin appears to be tender to touch, signs of bruising/bleeding are noted, or the area seems indurated or erythematous. If locating injection sites on the abdomen, avoid giving the injection in the umbilicus, ribs, or hip bone. If injecting in the thighs, use the outer areas, below the groin and above the knee. Subjects will be semirecumbent during dosing until requested to stand for orthostatic BP and pulse measurements. For additional information on study drug administration, please refer to the study pharmacy manual.

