Study Primary Objective: 
Part 1:
To characterize the safety and tolerability of single SC doses of TAK-510 in healthy subjects.Part 2:
To characterize the safety and tolerability of multiple SC doses of TAK-510 in healthy subjects.Part 3:
To characterize the safety and tolerability of multiple SC dose regimens of TAK-510 that include titration from lower doses in healthy subjects. Secondary Objectives: 
Part 1:
To characterize the PK of TAK-510 in plasma following single SC doses in healthy subjects.To assess the immunogenicity of TAK-510 following single SC doses in healthy subjects.To characterize the PK of TAK-510 in urine following single SC doses in healthy subjects.Part 2:
To characterize the PK of TAK-510 in plasma following multiple SC doses in healthy subjects.To assess the immunogenicity of TAK-510 following multiple SC doses in healthy subjects.	

– To characterize the PK of TAK-510 in urine following multiple SC doses in healthy subjects. 
• Part 3:
– To characterize the safety and tolerability of single SC rechallenge doses of TAK-510 after a washout from multiple SC dose regimens that include titration from lower doses in healthy subjects.– To assess the immunogenicity of TAK-510 following multiple SC dose regimens that include titration from lower doses, washout, and redosing in healthy subjects.	

Study Subject Population: Healthy male and female (nonchildbearing potential only) subjects aged 18 to 55 years, inclusive, at screening. Body mass index ≥ 18 and ≤ 30.0 (kg/m^2) at the screening.
	
Planned Number of Subjects: 
Part 1: Up to approximately 136 subjects. Part 2: Up to approximately 64 subjects. Part 3: Up to approximately 24 subjects. Approximate values do not account for potential replacement of subjects who withdraw for nonsafety reasons.
	Planned Number of Sites: 
Up to 2 sites.

Dose Levels: 
Part 1: TAK-510 SRD: starting dose 5 μg Part 2: TAK-510 MRD: doses to be determined based on Part 1. Part 3: TAK-510 Dose Titration and Redosing: doses to be determined based on Parts 1 and 2.
	Route of Administration: 
Subcutaneous (SC)

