^e All BP and pulse assessments should be made in duplicate, and the average of both assessments should be used to calculate the final result. The investigator can take a third measurement if there is inconsistency (ie, a difference >10 beats per minute in heart rate or a difference >10 mm Hg in systolic or diastolic BP) between assessments (see Section 9.2.4 for details). If 3 measurements are obtained, the final BP readout should be the average of the 2 more consistent assessments. On Day -1, vital signs will be time-matched (± 5 minutes) to the Day 1 clock time (ie, time-matched baseline). At predose, vital signs will be measured within approximately 1 hour before the first dose. All BP and pulse assessments must be completed before PK blood sampling.

^f At least 24 hours of continuous telemetry monitoring will be conducted between check-in on Day -2 and predose on Day 1.

^g Predose time-matched telemetry extractions may take place between Day -2 and Day -1 in conjunction with the 24-hour predose continuous telemetry.

Table 3.f Part 3 for Dose Titration and Redosing Cohorts 18 to 20: Screening Through Day 15, Follow-Up, and ET

	Days															ET	
	Screen			Dosing							8 (Dis-charge)	9 to 13 Wash out ^b	Day 13 ±1 day (Confine again)	Day 14 ±1 day (Single Dose)	Day 15 ±1 day (Dis-charge)	Follow-up Visit Day 29 ±3 days	
	-28 to -3	-2 ^a	-1	Pre dose	1	2	3	4	5	6							

^b Dosing regimen for TAK-510/placebo will be determined based on data from Part 1.

ⁱ Safety laboratory will include hematology, serum chemistry, and urinalysis parameters. During Part 3, if an LFT is elevated, a repeat test should be performed before the next dose of study drug is administered.

^j If CK is elevated in an individual subject after dosing, additional serum samples for CK may be collected at the investigator's discretion. The medical monitor will be updated regularly on any findings of elevated CK and plans for continued monitoring.

^k Glucose finger stick will be performed at predose and ~1 hours postdose on each day.

^l Hepatitis panel, including HBsAg and anti-HCV.

^m Serum pregnancy tests for female subjects only.

ⁿ An FSH level will be obtained to assess postmenopausal status.

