Optional DNA samples will also be collected from subjects that provide consent for collection through a separate procedure. DNA samples can be collected at any time on the day of discharge (Day 8) or at early termination (if applicable). Subjects will be discharged on Day 8 and will be readmitted the evening prior to redosing. After a 7-day washout (168 hours after the last dose of the 7-day treatment period), subjects will be dosed with a single dose of study drug (ie, at the same dose and double-blind treatment assignment as their highest daily dose during the 7-day treatment period). The duration of washout may be subject to change based on emerging safety, tolerability, and available PK data. Subjects will be confined the evening prior to redosing and for at least 30 hours after their redosing, while not being confined for the entire washout period. Subjects will return after discharge for additional immunogenicity and other assessments at follow-up visits on Day 29. Based on emerging safety, tolerability, and available PK data, subjects may be confined during washout at the discretion of the investigator in consultation with the sponsor and medical monitor.

In Part 3, up to 3 cohorts may be dosed sequentially for 7 days using a dose titration design of 1 to 5 days at lower doses followed by 2 to 6 days at the highest dose for that cohort, which will not exceed the dose studied in the highest completed dose cohort in Part 2. Cohorts 18 and 19 may be started in parallel. The proposed dose titration designs for the 3 cohorts are as follows:

Cohort 18: Single doses that escalate on a daily basis will be given on the first 2 to 5 days of the 7-day dosing period, followed by a maximum daily dose on the remaining days of the 7-day dosing period.

Cohort 19: A lower starting dose will be given on the first 2 to 3 days of the 7-day dosing period, followed by a maximum daily dose for the remaining days of the 7-day dosing period. The lower starting dose is to be determined based on Cohort 18.

Cohort 20: The initial daily dose(s) are to be determined by Cohorts 18 and 19 and will be given on the first 1 to 3 days, followed by the maximum daily dose for the remaining days of the 7-day dosing period. The maximum daily dose will be the same as that Cohorts 18 and 19, or higher as supported by safety, tolerability, and PK data from at least the same daily dose (or higher) in Part 2 MRD cohorts.

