Dose regimens up to the current planned maximum exposure level (AUC_∞) of 705,000 h*ng/mL will be studied as determined by the prior dosing regimen in Part 2. The daily exposure will not exceed an exposure established as well tolerated in Part 2. Doses in Part 3 are planned to be administered SC once daily. Based on emerging PK data from Parts 1 and 2, and PK data from prior cohorts in Part 3, adjustments to dose and to repeat dosing duration may be implemented.

The dose escalation meeting will determine the doses and dose schedule of Cohort 18 and 19 based on safety, tolerability and available PK data from Parts 1 and 2. After completion of Cohort 18 and 19, and before selecting the next dose schedule, a blinded assessment of the safety and tolerability, laboratory results of at least 24 hours after the last dose in the cohort, and available PK data will be analyzed in the dose escalation meeting (composed of representatives from the sponsor and site study teams).

The blind may be broken for select sponsor representatives before each blinded cohort review and/or dose escalation meeting, if necessary, due to safety concerns based on the prospectively prepared unblinding plan. Following each blinded dose cohort review and after dose escalation decisions have been made, the sponsor may be unblinded using the prospectively prepared unblinding plan.

Subjects who drop out may be replaced at the discretion of the sponsor after discussion with the investigator.

Study Drug Administration

In Part 3, when administering TAK-510, injection sites must be rotated. [REDACTED]. The single SC dose of TAK-510 should be administered in the abdomen first (at least 2 cm away from the umbilicus), followed by upper arms, then thigh as alternative sites, avoiding areas of scars, moles, tattoos, or other irritated skin (eg, vitiligo, eczema, etc). If repeat injections of TAK-510 are given in the same spot, this

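### Does the protocol name conflicting sources for the Part 3 doses, and for Cohort 19 in particular?

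*Protocol*

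**What the plan says.** Four places in the protocol bear on the source of the Part 3 doses.

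- **Section 1.0, Dose Levels, Part 3:** "TAK-510 Dose Titration and Redosing: doses to be determined based on Parts 1 and 2".
- **Section 3.3.1, Table 3.f** (Cohorts 18 to 20), footnote to the study drug administration row: "Dosing regimen for TAK-510/placebo will be determined based on data from Part 1". Table 3.b, the Part 2 schedule in Section 3.2.1, carries the same sentence.
- **Section 6.1.4, description of Cohort 19:** "The lower starting dose is to be determined based on Cohort 18". Just before the cohort descriptions it says: "Cohorts 18 and 19 may be started in parallel".
- **Section 6.1.4, dose escalation meeting:** the meeting determines the "doses and dose schedule of Cohort 18 and 19 based on safety, tolerability and available PK data from Parts 1 and 2". The next review is placed after both cohorts are complete.

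Section 6.1.4 also sets limits. The highest dose of each Part 3 cohort is one "which will not exceed the dose studied in the highest completed dose cohort in Part 2", and "The daily exposure will not exceed an exposure established as well tolerated in Part 2".

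**The concern.** Read one after another, these statements seem to give three answers to one question: Part 1 alone, Parts 1 and 2, or Cohort 18. The question matters because Section 6.1.4 allows Part 3 to begin before Parts 1 and 2 have finished. The named source then tells the sponsor and the site which results must be available before doses are chosen. Part 1 gives each subject one dose, whereas Part 3 gives seven daily doses and a later single redose, so a schedule that mentions only Part 1 appears to leave out the repeat-dose evidence.

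The Cohort 19 sentence adds a problem of timing. If Cohort 19 depends on what is seen in Cohort 18, it is hard to see how the two can start together. If doses were set on data that could not yet exist, or without Part 2 data, that would be a real defect in a first-in-human study.

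**Working it through.** No sample size, power or error rate is involved, and the protocol gives no figure to reproduce. The check compares the texts and adds a short day count.

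**1. What each statement covers.** Section 1.0 and Table 3.f speak of Part 3 as a whole. The meeting paragraph in Section 6.1.4 covers the doses and schedule of Cohorts 18 and 19. The Cohort 18 sentence covers only the lower starting dose of Cohort 19, not its maximum dose. Section 1.0 and the meeting paragraph agree with each other. That leaves two separate questions: the footnote, and the Cohort 18 sentence.

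**2. The footnote.** It names Part 1 but does not say that Part 1 is the only source. Part 1 is a genuine input to Part 3: Section 6.3.2.4 bounds the regimens of Parts 2 and 3 by an AUC∞ of 705,000 h*ng/mL or the highest AUC∞ tolerated in Part 1. The sentence is identical to the one in Table 3.b, where Part 1 is the only earlier part, so carry-over is the likely explanation. That is an inference.

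**3. The Cohort 18 sentence, sequential start.** Section 6.1.4 describes up to three sequential cohorts, and the parallel start is optional. In sequence, a general source (Parts 1 and 2) and a later refinement from Cohort 18 fit together. Section 6.1.4 allows for this in a sentence that ends: "PK data from prior cohorts in Part 3, adjustments to dose and to repeat dosing duration may be implemented". Sections 8.1.3 and 11.2 also provide for a blinded review after each cohort.

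**4. The Cohort 18 sentence, parallel start.** Assume that both cohorts start on the same day.

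- Cohort 19 receives its lower starting dose on the first 2 to 3 days, so at the latest on Day 3.
- The review needs laboratory results from at least 24 hours after the last dose in the cohort. From the Day 7 dose the earliest day is 7 + 1 = Day 8. From the Day 14 redose it is 14 + 1 = Day 15.
- Both fall after Day 3, so reviewed Cohort 18 results cannot inform that dose.
- For the review to come before Cohort 19's Day 1, Cohort 19 would have to start at least 8 − 1 = 7 days, or 15 − 1 = 14 days, after Cohort 18.

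Under a same-day start the sentence can therefore refer only to Cohort 18's planned doses. The text does not say so, but nothing rules it out: the sentence does not mention results or data, and the meeting sets both cohorts' doses.

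**5. What holds under every reading.** The maximum dose in each Part 3 cohort is limited to that of the highest completed Part 2 cohort, and daily exposure to one well tolerated in Part 2. Cohort 19's lower starting dose lies below its own maximum, so it falls under the same limit. Neither limit can be applied without Part 2 data, whatever Table 3.f says. The interruption criteria in Section 6.2.2 apply throughout.

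**6. Effect on the analysis.** Sections 6.1.4 and 6.3.1 make the comparison of Part 3 with Parts 1 and 2 descriptive. Section 11.1.4 summarises Part 3 by dose regimen, and Section 11.3 plans no hypothesis test. None of these depends on which data informed the choice of dose.

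**7. Reach.** The footnote applies to 3 × 8 = 24 subjects, 3 × 6 = 18 of them active. The Cohort 18 sentence applies to 8 subjects, 6 active, and is unclear only if the parallel option is used. These are cohort sizes, not numbers of subjects whose dose would change.

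**The case for a change.** The case for amending is that site staff work from the schedule tables, and Table 3.f does not match the body of the protocol. The wording for Cohort 20, whose initial doses depend on Cohorts 18 and 19, is followed by a review after those cohorts. It is natural to read the Cohort 19 sentence in the same way, as meaning results. No condition ties the parallel option to that sentence, and the section calls the cohorts sequential while permitting a parallel start. Correcting one footnote and one clause would cost almost nothing.

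Most of this is right as a description of the text. The footnote omits Part 2, and the meaning of the Cohort 18 sentence under a parallel start is not stated. What does not follow is that a decision could go wrong because of it. The dose escalation meeting, not the footnote, determines the doses of Cohorts 18 and 19, and its stated basis includes Part 2. The impossibility in the day count needs both a same-day start and a reading of the sentence as results, and the protocol commits to neither.

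**Conclusion.** The inconsistency in wording is real, but it is minor and calls for no change to the plan. It consists of one footnote, probably carried over from Table 3.b, and one clause that is unclear only under an optional start. The Part 2 limits on dose and exposure in Section 6.1.4 bind under every reading. Rewording would alter no dose limit, visit, sample, safeguard or analysis that can be identified from the protocol. If the protocol is opened for another reason, Section 1.0, Table 3.f and Section 6.1.4 can be reconciled then; which source governs is for the sponsor and the investigator to decide.

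The conclusion rests on two assumptions: that the dose escalation meeting applies the Section 6.1.4 limits as written, and that the schematic in Figure 2.a, which is not reproduced in the available copy, says nothing to the contrary.

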6.2 Stopping Rules

6.2.1 Stopping Criteria for Individual Subjects

Subjects will permanently discontinue study drug for any study drug-related adverse events that are rated Grade ≥ 3 in severity on the National Cancer Institute (NCI) Common Terminology Criteria for Adverse Events (CTCAE) scale (v5.0).

6.2.2 Criteria for Premature Termination or Suspension of the Study

The study will be completed as planned unless one or more of the following criteria are satisfied that require temporary suspension or early termination of the study:

- Any subject experiences a Hy's Law reaction (defined as alanine aminotransferase [ALT] or aspartate aminotransferase [AST] $>3 \times$ the upper limit of normal [ULN] in conjunction with elevated total bilirubin $>2 \times$ ULN without findings of cholestasis or other alternate etiology).
- New information or other evaluation regarding the safety or efficacy of the study drug that indicates a change in the known risk profile for TAK-510, such that the risk is no longer acceptable for subjects participating in the study.
- Significant violation of Good Clinical Practice (GCP) that compromises the ability to achieve the primary study objectives or compromises subject safety.
- The sponsor elects to terminate or suspend the study for administrative reasons including plans to modify, suspend, or discontinue development of the study drug.

In addition, the study may be interrupted for review of the safety data during Parts 1, 2, or 3 if one of the below criteria is met:

- Two or more subjects experience a sinus tachycardia with HR >120 bpm at rest while semirecumbent with symptoms of palpitation or lightheadedness requiring medical intervention and considered related to TAK-510, or
- Two or more subjects experience a CTCAE v5.0 Grade ≥ 3 hypotension (ie, requiring medical intervention) and considered related to TAK-510, or
- One subject experiences a CTCAE v5.0 Grade ≥ 3 syncope (fainting or orthostatic collapse) and considered related to TAK-510, or

- Two or more subjects experience a CTCAE v5.0 Grade 3 event considered related to TAK-510 administration, or
- One subject experience a CTCAE v5.0 Grade 4 event considered related to TAK-510 administration, or
- One subject with ALT or AST $>5 \times$ ULN after TAK-510 administration, or
- One subject with ALT or AST $>3 \times$ ULN with appearance of fatigue, nausea, vomiting, right upper quadrant pain or tenderness, fever, rash, and/or eosinophilia ($>5\%$), or
- One subject with increases in creatinine $>1.5 \times$ ULN after TAK-510 administration, or
- One subject with a serious adverse event (SAE) considered related to TAK-510 administration, or
- Two or more subjects experience a CTCAE v5.0 Grade ≥ 2 injection site reaction (defined as pain combined with lipodystrophy and/or edema).

If a safety concern is identified after review of the data, the investigator and/or the sponsor may consider potential changes in the next planned dose level. Possible changes in dose administration include, but are not limited to:

- Administration of an intermediate dose between the current and next planned dose.
- Repeated administration of the current dose.
- Administration of a lower dose than the existing dose levels.
- Study termination.

Study drug dosing may resume if the event is considered unlikely to be related to treatment with study drug by the investigator and sponsor.

During Study Drug Dosing in Part 2 (MRD)

If the criteria for pausing occurs in SRD Part 1 at a higher level than is being dosed in MRD Part 2, dosing in Part 2 may continue provided it is at a lower daily dose than in Part 1 than that at which the event was observed, and the sponsor and investigator agree after careful review of the totality of the available blinded data.

During Study Drug Dosing in Part 3 (Titration and Redosing After Washout)

If the criteria for pausing occurs in MRD Part 2 or SRD Part 1 at a higher level than is being dosed in Part 3 (ie, higher level than the maximal dose during titration or Day 14), dosing in Part 3 may continue provided it is at a lower daily dose than in Parts 1 or 2 than that at which the event was observed, and the sponsor and investigator agree after careful review of the totality of the available blinded data.

6.3 Rationale for Study Design, Dose, and Endpoints

6.3.1 Rationale of Study Design

A randomized, double-blind, placebo-controlled design for Part 1 is considered adequate to characterize the safety, tolerability, and PK of single doses of TAK-510.

Part 2 of the study is a randomized, double-blind, placebo-controlled, sequential panel MRD study where up to 8 cohorts may be studied under repeat-dose conditions.

The intention with the dose titration part of Part 3 is to provide an exploratory evaluation to assess the safety and tolerability profile of dose titration at the start of the 7-day treatment period. This comparison will be descriptive (ie, without hypothesis testing) versus tolerability findings in Parts 1 and 2 with comparable exposures to determine whether dose titration results in different tolerability. The redosing part of Part 3 is intended to provide an exploratory evaluation to assess the effects of a single dose (after 7 days [168 hours] of washout following the 7-day treatment period) on vital signs, adverse events, and other safety parameters.

6.3.2 Rationale for Dose

The starting dose for this FIH study is 5 µg. The 4 considerations for the selection of the starting dose for the FIH study are summarized here and described in more detail below:

1. Nonclinical safety data and Food and Drug Administration (FDA) maximum safe starting dose guidance [10].
2. Nonclinical cardiovascular safety pharmacology data for TAK-510.
3. Benchmarking to [REDACTED] cardiovascular findings.
4. Lowest projected antiemetic effect and insulin secretion effect as demonstrated in nonclinical species.

6.3.2.1 FIH Starting Dose Consideration Based on Nonclinical Safety Study Results, Published [REDACTED] Results, [REDACTED] Experience

The principle of the FDA Guidance “Estimating the Maximum Safe Starting Dose in Initial Clinical Trials for Therapeutics in Adult Healthy Volunteers” [10] is to use a 10-fold safety factor on the no-observed-adverse-effect level (NOAEL) from nonclinical data to identify a starting clinical dose.

For TAK-510, NOAELs were identified in the 2-week GLP-compliant, repeat-dose toxicity studies, and no-observed-effect levels (NOELs) were identified in the respiratory and central nervous system safety pharmacology studies.

The NOAEL in the rat was 60 mg/kg (highest dose investigated); minimal body weight loss and dose-dependent minimal to moderate vacuolation of the proximal convoluted tubule of the kidney (without degeneration/necrosis or changes in clinical pathology) were considered nonadverse. The NOAEL in the dog was 15 mg/kg; body weight loss and associated clinical observations were considered adverse at 50 mg/kg. [REDACTED]

However, cardiovascular effects in dogs were the principal finding in the safety pharmacology studies. In this study, the lowest dose of [REDACTED] TAK-510 produced a transient increase in HR and a transient decrease in BP, and a NOEL was not identified.

Given the reversible nature of the cardiovascular changes, and the lack of other significant safety findings at this dose level, the [REDACTED] TAK-510 dose is not anticipated to result in any clinically significant effects or significant safety risk. [REDACTED]

[REDACTED] Incretin effects were as expected with transient, glucose-dependent increases in both insulin and glucagon reported. Cardiovascular effects were consistent across studies with an increase in HR and decrease in BP reported during the 2 to 4 hours of infusion. [REDACTED]

Additionally, the lowest dose tested [REDACTED] in the first-in-human clinical study of [REDACTED] resulted in changes in BP (diastolic BP changes at 30 minutes) that were not considered clinically significant. [REDACTED]

[REDACTED] Refer to the current edition of the TAK-510 Investigator's Brochure for additional details of FIH study findings [REDACTED].

The selected FIH dose [REDACTED] and derived from a combination of nonclinical and clinical cardiovascular profiles in which submaximal or minimal cardiovascular changes, respectively, were reported. [REDACTED]

In summary, given the totality of these findings from nonclinical safety, published literature, and nonclinical pharmacology, the proposed starting dose is 5 μ g.

